7.1. Statistical Methods Supporting the Primary Objective

The Primary Objective of this study is to determine the impact of GC test result on adjuvant treatment decisions compared to clinical factors alone. This will be evaluated by testing for an effect of GC score in a regression model which adjusts for CAPRA-S risk score. As a cluster-crossover trial, a generalized linear mixed effects model will be used to model the probability of a subject receiving adjuvant treatment within center, in a specific period of the study. Since GC score is a subject-level covariate, an individual-level regression model is utilized rather than a cluster-level aggregated analysis (Campbell 2014, Chapter 6). Specifically, the model to be fit is

$$\text{logit}\left(\frac{\pi_{ijk}}{1-\pi_{ijk}}\right) = \beta_0 + \beta_1 G_i + \beta_2 (G_i * GC_i) + \beta_3 \text{CAPRA-S}_i + \gamma_j + \phi_k$$

where π_{ijk} is the probability of treatment for the i^{th} subject enrolled in the j^{th} cluster (ie: center) during the k^{th} period, G_i is the group to which the subject is enrolled (GC=1, UC=0), CAPRA-S_{*i*} is that subjects' CAPRA-S score (0-12), GC_{*i*} is the GC score (0-1), $\beta_0 \sim N(\mu, \sigma^2)$ and

$\phi_k \sim N(0, \sigma^2)$ are random cluster and period effects, respectively. The null hypothesis $\beta_2 = 0$ will be tested using a Type III test (SAS PROC GLIMMIX) at a 0.05 significance level. 95% confidence intervals using robust variance estimates will also be calculated.

In addition to the model described above, an additional model including a group-by-period interaction term will be fit to ensure that group assignment in a period is not effected by preceding or subsequent periods. For the purposes of this analysis, the period effect will be

considered fixed. This may detect carry-over effects if behaviors or attitudes of physicians within sites persist or change over the course of the study or if changes in patient education materials or their presentation change from one period to the next. Should this interaction term be significant, an alternative analysis utilizing non-consecutive periods may be used.

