7.3. Statistical Methods Supporting the Secondary Objectives

All tests will be two sided at a 0.05 significance level. Individuals who are lost to follow-up will be considered censored in time to event analyses. Treatment plans available at the time of drop-out will be considered the final treatment plans.

Secondary Objective 1: To determine whether the net benefit to subjects in the GC arm is superior to the UC arm. This will be determined by directly calculating the net benefit (Vickers and Elkin 2006) across a range of treatment thresholds, Decision Curve Analysis (DCA). DCA is a method for assessing prognostic models that incorporates clinical consequences and the potential probability thresholds at which the likelihood of a given outcome (eg: progression to metastatic disease) may influence the treatment decision of a patient and their physician. For example, one individual may choose treatment if there is a 5% chance of a given outcome while another individual may not be influenced unless the likelihood of that outcome is as high as 10 or 15%. Thus, this methodology allows for how different patients may differentially weigh false negative or false positive results. The calculated net benefit is plotted against threshold

probabilities, and different prediction tools (eg. CAPRA-S and GC) can be compared across these probabilities. If GC is not superior to UC across all thresholds, the region of superiority will be evaluated to determine if it contains a clinically meaningful ratio of harm due to unnecessary treatment versus missed treatment.

Secondary Objective 2: To determine whether use of the GC test result results in decreased likelihood of treatment for CAPRA-S high and increased likelihood of treatment for CAPRA-S low, a modeling approach similar to that of supporting the Primary Objective will be used, but with a GC-by-CAPRA-S interaction term as follows:

$$\text{logit}\left(\frac{\pi_{ijk}}{1-\pi_{ijk}}\right) = \beta_0 + \beta_1 G_i + \beta_2 (G_i * GC_i) + \beta_3 CAPRA-S_i + \beta_4 (G_i * CAPRA_i * GC_i) + \gamma_j + \phi_k$$

where parameters are defined as previously. The test of $H_0: \beta_4 = 0$ will be performed using a Type III test (SAS PROC GLIMMIX). The direction of the interaction will be evaluated graphically with the probability of treatment based on the model and for empirical probabilities using pre-defined GC and CAPRA-S cutoffs.

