Secondary Objective 3: Time-to salvage therapy initiation will be modeled using a Cox formulation of a Frailty regression model with a similar formulation (ie: main and random effects) to that used for the primary analysis. Kaplan-Meier curves for GC and UC arms will be plotted, as well as for combinations of high- and low-risk GC and CAPRA-S groups.

Secondary Objective 4: Time-to BCR and metastatic progression will be evaluated similarly to the model described for Secondary Objective 3.

Secondary Objective 5: Summary statistics for all QOL instruments and corresponding confidence intervals will be calculated and compared for the GC and UC subjects and shown graphically over time. Validated instruments are used to measure erectile function, urinary function, sexual interest, and sexual satisfaction. Scores for each domain will be scaled with a minimum to maximum range of 0-100. Comparisons between GC and UC subjects will be made at each timepoint (3, 6, 12 and 24 months after surgery) and on each domain and overall score (VAS 0-10), using an ANCOVA analysis including adjustment for time since surgery. Should the assumptions for ANCOVA not be met (strongly skewed data or substantial ceiling or floor effect) a semiparametric ANCOVA model will be used (as in Buja 1989) to adjust for time-from surgery. If the distribution of time-from surgery is similar in the two groups, a Mann-Whitney test for differences will be used to corroborate the ANCOVA model. For this secondary objective, there will be no adjustment for multiple comparisons across domains or time points.

Exploratory Objective: Using a variety of budget models the cost of care for patients in the GC vs. UC arms will be compared out to 3 years from surgery. This will include estimated costs for adjuvant therapy. Differences in total cost, and differential cost per patient (UC vs GC) will be calculated and compared using either standard t-tests if data is normally distributed or appropriate non-parametric test if data is right skewed.

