In other clinical utility studies on GC (eg: Badani 2014) physicians reviewed several cases. With physicians as clusters, the ICC in this study is approximately 38% using methods of Wu (2012). In somewhat different scenarios, and with alternative methods of calculation Adams (2004) identified the IQR of ICCs as 3.5-28.4% in cluster-randomized trials. Assuming that the ICC for an entire clinical center will be less than for a single physician, and given the findings of Adams, an ICC of 23% was selected for the simulation – given the other parameter settings of the model, specified above, this is equivalent to setting $\rho^2 = 1$. A small intra-period (across sites) is also incorporated (ICC = 3%) to include the possibility of a temporal correlation across sites - potentially related to changes in educational materials or seasonal trends.

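### QOL and cost are tested without center, period or center-by-period terms although arms are assigned by center-period, and early QOL scores may precede enrolment

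*Combined protocol and SAP*

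**What the plan says.** Section 3 gives each center one strategy (GC or UC) for 3 months at a time. Under Section 3.1 a subject takes whichever arm the center holds at enrolment. The primary model in Section 7.1 follows this design: its last two terms "are random cluster and period effects, respectively". Secondary Objective 2 repeats those terms, and Objectives 3 and 4 say they take over the same formulation.

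Section 7.3 states "All tests will be two sided at a 0.05 significance level". QOL (Secondary Objective 5) is compared at 3, 6, 12 and 24 months after surgery, by domain and overall, "using an ANCOVA analysis including adjustment for time since surgery". A semiparametric version is used if assumptions fail. If time from surgery is similarly distributed in the two groups, "a Mann-Whitney test for differences will be used to corroborate the ANCOVA model". Cost (Exploratory Objective) is "compared using either standard t-tests if data is normally distributed or appropriate non-parametric test if data is right skewed". No center, period or center-by-period term and no robust variance is named for either outcome.

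On timing, Section 4.1 (item 5) admits subjects up to 1 year after RP, while Section 5.2 (item 5) counts QOL visits from surgery. Sections 5.3 and 7.3 also count cost from surgery.

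**The concern.** Subjects enrolled in one center during one quarter share an arm. They also share whatever else is particular to that center and quarter. A test that treats them as independent uses the wrong variance for the arm difference. The plan expects change over time: Section 7.1 checks for carry-over "if behaviors or attitudes of physicians within sites persist or change over the course of the study", and Section 7.5.1 builds a 3% intra-period correlation across sites into the power simulation. A t-test or Mann-Whitney test has no place for such terms, so the omission cannot be read as shorthand.

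The second issue is timing. A QOL score recorded before enrolment cannot reflect GC use, and nothing in the text restricts the comparison to later scores or treats the earlier ones as baseline.

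At stake are the p-values and intervals for Objective 5 and for cost, and the size of the early QOL differences.

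**Working it through.** **The plan's own ICC.** Section 7.5.1 equates a site ICC of 23% with a random-effect variance of 1. On the logistic scale, 1/(1 + π²/3) = 1/4.29 = 23.3%, which agrees. This ICC and the 3% period ICC were chosen for receipt of treatment. None is given for QOL or cost, so every ICC below is an assumption.

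**Formula, equal cells.** Inputs from Section 3: 550 subjects, 14 centers, 2 GC and 2 UC periods each. That is 14 × 4 = 56 center-periods with m = 550/56 = 9.8 subjects. Let ρw be the ICC within a center and period, and ρb the ICC within a center across periods. The variance of the arm difference relative to independence is DE = 1 + (m − 1)ρw − mρb. The true level of a nominal 5% test is 2 × (1 − Φ(1.96/√DE)). With ρw = ρb, DE = 1 − ρ, which is below 1: stable center effects cancel. With 0.10/0.05, DE = 1 + 0.882 − 0.491 = 1.391.

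**Simulation, unequal centers.** Null trials used the monthly site means in Section 7.5.1 scaled to the stated number of scores (site 5 is not listed; 4 or 5 assumed), blocks of 2 or 4, 4 periods and a normal outcome. Ranges cover repeated runs, with Monte Carlo error of 0.3 to 0.9 points.

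| ρw/ρb | Scores | DE | Level by formula | Level simulated, unclustered test |
|---|---|---|---|---|
| 0.05/0.05 | 550 | 0.95 | 4.4% | 4.4-5.6% (equal ICCs 0.01-0.10) |
| 0.05/0.025 | 550 | 1.196 | 7.3% | 8.5-9.3% |
| 0.10/0.05 | 550 | 1.391 | 9.7% | 13.0-14.7% |
| 0.10/0.05 | 275 | 1.146 | 6.7% | 8.7-9.2% |
| 0.10/0.05 | 138 | 1.023 | 5.3% | 6.8-7.3% |
| equal ICCs plus 3% period variance | 550 | n/a | n/a | 9.0-10.8%, mostly 9-10% |

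Simulation exceeds the formula because the largest centers have large cells: 550 × (10/58)/4 ≈ 24 against a mean of 9.8. If enrolment spreads over 8 periods, the level is 7.1-7.7% with equal ICCs and 3% period variance, and 5.9-9.1% with ρb half of ρw and no period effect.

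**Alternatives at 0.10/0.05, 550 scores.** Individual-level fixed center and period terms: 12.9%. Regression of weighted center-period means: 6.6%. Mixed model with a random center-by-period effect: 5.1%. With equal ICCs, center and period terms alone give 4.3-5.8%.

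**Skewed cost.** Lognormal, log-scale SD 1, 8 ICC and period settings: t-test 4.8-10.5%, Mann-Whitney 4.6-13.1%, weighted center-period means on raw cost 4.9-6.4%.

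**Pre-enrolment scores.** The enrolment distribution is not given. Share f preceding enrolment:
- All enrol within 3 months of RP: 0% at both visits.
- Uniform over 0-6 months: (6 − 3)/6 = 50% at month 3, 0% at month 6.
- Uniform over 0-12 months: (12 − 3)/12 = 75% at month 3, (12 − 6)/12 = 50% at month 6.

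If the arms are otherwise comparable, the visible effect is the true effect × (1 − f). An illustrative 5-point month-3 effect shows as 5.0, 2.5 or 1.25 points. A comparison with 80% power has Φ(2.80 × (1 − f) − 1.96) left: 29% at f = 0.50 and 10% at f = 0.75. If instead there is no GC effect, late enrollers score 5 points differently, and they make up 75% of one arm and 50% of the other, the arms differ by 5 × 0.25 = 1.25 points, in either direction.

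**The case against.** **The crossover protects the test.** It does against stable center effects. In a balanced layout with equal ICCs the unclustered test is even conservative: 4.4% at ICC 0.05, 3.9% at 0.10, 2.5% at 0.23. A reader might infer that ignoring center clustering inflates error as it does in a parallel cluster trial. The documents do not support that; only shared period effects and center-by-period variation do harm here.

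**The sizes are assumed and shrink with missing scores.** This stands. No QOL or cost ICC is given, and the larger figures need nearly all 550 subjects to give a score at the visit. If pre-enrolment scores are dropped, the early comparisons could have 275 or 138.

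**QOL is not offered as error-controlled evidence.** Section 7.3 disclaims multiplicity adjustment across domains and visits: four domains plus an overall score at four visits is 20 tests. This lowers the stakes, but does not justify a wrong variance within each test.

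**The covariate may already handle late enrolment.** Section 7.3 asks whether time from surgery is similarly distributed in the arms, which makes more sense for surgery-to-enrolment time than at fixed visits. On that reading the covariate could reduce a late-enroller shift. It would not undo the dilution.

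**The timeline figure may narrow the window.** Figure 2 is not shown, so this cannot be excluded. It limits confidence in the timing part only.

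**Conclusion.** The point stands for both analyses. The omission of center, period and center-by-period terms is plain in the text and applies at every QOL visit, so the 0.05 level is not assured. Its numerical effect depends on assumed ICCs: about 5% with center effects only, roughly 9-10% with 3% period variance, and about 13-14% at 0.10/0.05 with 550 scores, less with fewer.

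The timing problem holds with moderate confidence. Month-3 and month-6 scores can precede enrolment, and so can a month-12 score at the edge of the window. The share is unknown; a reader might take 75% and 50% as estimates, but they follow only from assumed uniform enrolment over a year. Cost counted from surgery likewise includes pre-enrolment cost. If that cost is balanced by arm, it adds noise and not bias to a difference in means.

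Two further inferences should be avoided. Copying the primary model's random effects would not be a full cure, because that model has no center-by-period term. Months 12 and 24 are not clear either: the test problem applies there too. The trial is unblinded and centers know the arm while enrolling, so differential recruitment of late enrollers could shift any visit.

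The primary analysis is unaffected by these points. QOL is secondary and cost exploratory, so the change is advisable, not critical.

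**What to change.** In Section 7.3:

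- **QOL, each visit.** Replace the unclustered ANCOVA and Mann-Whitney test with a linear mixed model: arm and period fixed, random center and center-by-period effects, and time since surgery kept and defined. Take denominator degrees of freedom at center-period level from the cells actually filled (filled cells − centers − periods). With all cells filled this is 56 − 14 − 4 = 38 for 4 periods or 112 − 14 − 8 = 90 for 8; with 138 scores and about 47 of 56 cells filled it is about 29. An alternative is a regression of center-period means on arm, center and period, weighted by cell size.
- **QOL timing.** Use only scores dated after enrolment as outcomes. Enter the last pre-enrolment score as a baseline covariate with a missing-baseline indicator. Report by arm how many scores at each visit precede enrolment.
- **Cost.** Compare mean cost with the weighted center-period-mean regression. Count cost from enrolment, or report pre-enrolment cost separately by arm.

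The cost is SAP wording; the analysis needs center, enrolment date and score date. Across the settings simulated with 550 scores, the mixed model had a level of 2.9-6.2%, so it can be conservative when there is no center-by-period variation. The weighted regression had 4.2-7.7%, slightly liberal when that variation is large. The mixed model was not simulated with the covariate or at the smaller numbers of scores. Intervals may widen, and the early comparisons lose subjects: from none to, under uniform enrolment over a year, 550 × 0.25 ≈ 138 left at month 3 and 550 × 0.50 = 275 at month 6. Scores after enrolment but before the GC report still count as exposed, so some dilution can remain.

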3.4. Clinical Data Collection

Where available, participating physicians in the study will be asked to provide the following clinicopathologic data in the provided case report form (CRF) for subjects meeting the inclusion criteria below. All data submitted to GenomeDx will utilize a case ID number and will be de-identified by the site prior to submission.

1. Ethnicity
2. Age at radical prostatectomy
3. Pre-operative PSA level: last pre-operative PSA level before radical prostatectomy
4. Lymph node status
5. Clinical and pathological stage
6. Clinical and pathological Gleason score (primary, secondary, and tertiary pattern if available)

7. Surgical margin status
8. Extra-prostatic extension
9. Seminal vesicle invasion
10. All available post-op PSA levels
11. Recommended treatment or management option for the patient after surgery
(detailed by type of treatment recommended)
12. Dates of actual treatments
13. Patient outcome

[figure not shown]

Figure 1: Study flow diagram

[figure not shown]

Figure 2: Patient flow timeline

4. Subject Eligibility

4.1. Inclusion Criteria:

Individuals satisfying all of the following criteria will be eligible to participate.

1. Prostate cancer patients who have undergone radical prostatectomy(RP)
2. PSA <0.1 ng/ml at enrollment
3. At least one of the following:
 - a. pT3 (SVI or EPE), **or**
 - b. Positive Surgical Margins
4. Tumor tissue (FFPE block) available for processing
5. RP within 1 year of enrollment
6. 18 years of age or older

4.2. Exclusion Criteria:

Individuals who satisfy **any** of the following criteria will not be eligible to participate.

1. Have regional or distant metastatic disease
2. Received any radiation or hormone therapy (neo-adjuvant, adjuvant, or salvage)
3. Node positive
4. Subjects who do not have banked specimens

5. Endpoints

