5.2. Secondary Endpoints

The following secondary endpoints will be utilized:

1. Time (from randomization) to adjuvant treatment administration
2. Time (from randomization) to salvage treatment administration
3. Biochemical Recurrence (BCR) at 3 years
4. Metastatic disease (regional or distant) at 3 years
5. QOL measures currently collected as part of the MUSIC-PRO initiative (<http://musicurology.com/pro/>) at 3, 6, 12, and 24 months after surgery

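### The QOL ANCOVA names only time since surgery as a covariate, which adds little precision, and nothing stops month-3 and month-6 scores dated before enrolment from counting as arm outcomes

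*Combined protocol and SAP*

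**What the plan says.** Section 7.3, Secondary Objective 5, sets out visit-by-visit tests: "Comparisons between GC and UC subjects will be made at each timepoint (3, 6, 12 and 24 months after surgery"), on each domain and on the overall score, "using an ANCOVA analysis including adjustment for time since surgery". If the ANCOVA assumptions fail, "a semiparametric ANCOVA model will be used (as in Buja 1989) to adjust for time-from surgery". A Mann-Whitney test corroborates the result "If the distribution of time-from surgery is similar in the two groups". For this objective no earlier score, age, CAPRA-S, center or period term is named, and no visit window is given.

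Section 5.2 takes the data from outside the trial, as "QOL measures currently collected as part of the MUSIC-PRO initiative", "at 3, 6, 12, and 24 months after surgery". It lists no pre-surgery or enrolment assessment. Section 4.1 admits men with "RP within 1 year of enrollment". Section 3.4 lists "Age at radical prostatectomy" among the CRF items (collected where available), and Section 3.3 provides a CAPRA-S report for every participant. Section 2.2 also asks whether the QOL effect differs by CAPRA-S risk group.

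**The concern.** There are two linked problems.

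- **Precision.** Each comparison is made at one visit counted from surgery, so time since surgery varies only through the timing of form return. It can remove little between-man variance. Variables more likely to do so (the man's own earlier score on the domain and, to a smaller degree, his age) are not named.
- **What is compared.** The visit clock starts at surgery, but the strategy is assigned at enrolment, up to a year later. A man who enrols at month 8 has month-3 and month-6 scores that the strategy cannot have affected. Nothing in Section 7.3 removes them from the arm comparison, where they pull the estimated difference toward zero.

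At stake are wider intervals than the collected data require at months 12 and 24, and diluted differences at months 3 and 6.

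**Working it through.** The documents give no SD, correlation, slope, visit window or power for QOL, so there is no plan figure to reproduce. Inputs from the documents are the four visits, the 0-100 scale, the one-year enrolment limit and N = 550. Everything else below is assumed and shown as a range. Clustering is ignored, so the precision figures are relative gains.

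**1. Variance explained by time since surgery.** R² = (slope × SD of visit timing / SD of score)². A uniform window of ±w months has SD w/√3.

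- Slope 4 points/month, score SD 25, ±1 month: (4 × 0.577/25)² = 0.9%.
- Same, ±2 months: (4 × 1.155/25)² = 3.4%.
- Slope 0.3 points/month (late follow-up), ±2 months: (0.3 × 1.155/25)² = 0.02%.
- Loose case, slope 5, timing SD 1 month, score SD 20: (5 × 1/20)² = 6.25%. Then 550 men act like 550/(1 − 0.0625) = 587.

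**2. Share of men with a score before enrolment.** The distribution of enrolment times is not given. If enrolment is uniform over the stated range after RP:

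| Enrolment range | Month-3 score predates enrolment | Month-6 score predates enrolment |
|---|---|---|
| 0-12 months | 75% | 50% |
| 0-6 months | 50% | 0% |
| 1-4 months | 33% | 0% |

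**3. Dilution if all scores are used.** If a share p of scores in each arm predates enrolment, a true difference δ among the other men has expected estimate (1 − p)δ. Under uniform 0-12 months that is 0.25δ at month 3 and 0.50δ at month 6.

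**4. Gain from the prior score.** If a share q of the men analysed has a prior score with correlation ρ to the outcome, and an indicator marks the rest, the variance ratio is 1 − qρ² and the SE falls by 1 − √(1 − qρ²).

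| q | SE reduction, ρ = 0.5 | SE reduction, ρ = 0.7 | 550 men act like |
|---|---|---|---|
| 25% | 3.2% | 6.3% | 587-627 |
| 50% | 6.5% | 13.1% | 629-728 |
| 75% | 9.9% | 20.5% | 677-870 |

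Simulation (3,000 trials per setting) gave variance ratios of 0.875 (ρ 0.5, q 50%) and 0.704 (ρ 0.6, q 75%), against 0.875 and 0.730 from the formula. Time since surgery alone gave 0.999-1.004. Age alone, at correlations 0.1-0.3, removes 1-9% of variance.

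**5. Where the gain falls.** A man whose month-3 score is post-enrolment enrolled before month 3 and has no earlier score on the listed schedule, so q = 0 at month 3. At month 6, only men enrolled between months 3 and 6 contribute a prior score. The table in step 4 applies in full at months 12 and 24.

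**6. Cost of using only post-enrolment scores**, uniform 0-12 months:

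- Month 3 keeps 25% of men, so the SE is 1/√0.25 = 2 times as large. The ratio of effect to SE still rises, from 0.25 to 1/2 = 0.50 (in units of δ over the full-sample SE).
- Month 6 keeps 50%, half of them with a prior score. The SE is √(0.875/0.5) = 1.32 (ρ 0.5) to √(0.755/0.5) = 1.23 (ρ 0.7) times as large. The ratio rises from 0.50 to 1/1.32 = 0.76 or 1/1.23 = 0.81.

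**The case against.** **The covariate has a purpose.** The condition on the Mann-Whitney test shows that time since surgery is there to handle timing differences between arms. A low R² does not make it a wrong choice. This stands, and it is a reason to keep the covariate.

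**Other covariates are not excluded.** The text says that the analysis includes this adjustment. A reader might infer that nothing else will be adjusted for, but the wording supports only that nothing else is named. That still matters: with several domains, four visits and no multiplicity adjustment, covariates are better fixed in advance.

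**No baseline QOL score is listed.** A reader might infer that a pre-enrolment score is in hand for every man, and so expect an SE reduction of 13-29% (q = 100%, ρ 0.5-0.7). The documents do not support this. Section 5.2 starts at month 3, and the share enrolling later is unknown. A share of 100% would require that nobody enrols before month 3, leaving no post-enrolment month-3 comparison.

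**The remedy widens some intervals.** True at month 3, and at month 6 if men enrol after it. Step 6 shows that the ratio of effect to SE still improves under the uniform assumption.

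**The inputs are assumed and individual-level.** Also true. The direction holds across the ranges tried, but the absolute gains do not carry over directly to a cluster-crossover trial.

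**Conclusion.** The point holds in limited form. Time since surgery is the only covariate named for the QOL ANCOVA, and at surgery-anchored visits it can explain little: about 0-3% of variance, and about 6% at the loosest inputs tried. Age and CAPRA-S are planned data items that go unnamed. Age alone adds little, and no figure is available for how far CAPRA-S predicts QOL.

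The weightier part is the pre-enrolment scores. Without a rule, some month-3 and possibly month-6 scores count as outcomes of a strategy not yet assigned. The share is unknown; under uniform enrolment over 0-12 months it would be 75% and 50%.

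A reader might infer that omitting the covariates biases the QOL comparison. It does not: the omission costs precision. The dilution comes from the pre-enrolment outcomes. This is one secondary objective, and the primary analysis is unaffected. The change is worth making because it needs no new data.

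**What to change.** In Section 7.3, Secondary Objective 5:

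- At each visit, analyse only scores dated after enrolment.
- For each domain, include arm, age at RP, CAPRA-S, the last MUSIC-PRO score on that domain before enrolment with a missing-score indicator, and center and period effects. Keep time since surgery as a minor covariate.
- State the visit windows, and say whether MUSIC-PRO holds a pre-surgery score. If it does, say whether it replaces the last pre-enrolment score.
- Report months from RP to enrolment by arm, with the number of men in each visit's comparison.

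The cost is SAP wording only. The downside is fewer men at the early visits: under uniform enrolment over 0-12 months, about 25% at month 3 and 50% at month 6, with wider intervals there. The prior-score gain is nil at month 3, partial at month 6, and falls mainly at months 12 and 24.

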2.2. Secondary Objectives

1. To determine whether the decision impact of the GC test is of benefit to patients. Specifically, is net benefit of GC use superior to those who do not have the GC test as assessed by decision curve analysis.
2. To determine whether use of the GC test results in decreased likelihood of adjuvant treatment for subjects with high CAPRA-S score (≥ 5) and increased adjuvant treatment for subjects with low CAPRA-S score (< 5). The hypothesis is that there is a non-zero interaction between GC test use and CAPRA-S.
3. To determine whether GC use is associated with earlier use of salvage therapies in CAPRA-S low risk patients and later use of salvage therapy in CAPRA-S high-risk patients.

4. To determine whether use of GC results in improved protection from BCR and metastatic progression.
5. To investigate the impact of GC use on QOL, and whether there is differential QOL impact among CAPRA-S high- and low-risk patients.
6. To determine whether collaborative-wide education and the use of CAPRA-S scores in the control group impacts rates of adjuvant radiotherapy compared to historical controls.

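### QOL (Secondary Objective 5) is tested 20 times, score by score and visit by visit, with no key contrast, no repeated-measures model, and forms that can precede enrolment

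*Combined protocol and SAP*

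**What the plan says.** Section 2.2 sets Secondary Objective 5: "To investigate the impact of GC use on QOL, and whether there is differential QOL impact among CAPRA-S high- and low-risk patients". Section 5.2 defines the endpoint as the MUSIC-PRO measures at 3, 6, 12 and 24 months after surgery. Neither section singles out a measure or a visit.

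Section 7.3 lists four domains: "Validated instruments are used to measure erectile function, urinary function, sexual interest, and sexual satisfaction". It adds an overall 0-10 score and says: "Comparisons between GC and UC subjects will be made at each timepoint (3, 6, 12 and 24 months after surgery) and on each domain". The method is ANCOVA adjusted for time since surgery. A semiparametric version is used if the data are strongly skewed or show ceiling or floor effects, and a Mann-Whitney test is added if time since surgery is similarly distributed in the two arms. The course over time is summarised and plotted, but not modelled.

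On error control, the same section opens with "All tests will be two sided at a 0.05 significance level" and closes the QOL paragraph with "For this secondary objective, there will be no adjustment for multiple comparisons across domains or time points".

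Section 4.1 allows enrolment up to one year after prostatectomy. Section 7.1 gives the primary model random center and period effects; the QOL ANCOVA names neither.

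**The concern.** Three features act together.

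- **No designated answer.** Objective 5 has 20 nominal p-values and no statement of which one, or which combination, answers it. A report could select whichever score and visit crossed 0.05.
- **Unused repeated measures.** Each test uses the forms from one visit only. A man's other scores contribute nothing, and a man without a form at that visit drops out of that comparison.
- **Visits timed from surgery, exposure timed from enrolment.** A man enrolled seven months after surgery completed any 3- and 6-month forms before his center's assigned strategy could reach him. As written, those forms enter the GC-versus-UC tests at 3 and 6 months, where they can only dilute a real effect or add noise.

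At stake is whether a reported effect of GC on QOL, or a reported absence of one, can be interpreted. The primary conclusion is not at stake.

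**Working it through.** The documents give no familywise error rate, power or sample size for QOL, so there is no stated figure to reproduce. The inputs are the per-test level and the number of tests.

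**Number of tests.** Section 7.3 gives 4 domains + 1 overall score = 5 scores, and 4 visits. 5 x 4 = 20 comparisons.

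**Expected false positives with no effect.** 20 x 0.05 = 1.0, whatever the correlation between tests.

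**Chance of at least one p<0.05, independent tests.** 1 - 0.95^20 = 0.64. This is an upper bound here, because the same men contribute at each visit and several scores are related.

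**Chance of at least one p<0.05, correlated tests.** The documents give no correlations, so they are assumed. I simulated 20 standard-normal test statistics (400,000 draws, |Z| > 1.96). Correlation was exchangeable between scores and between visits, and the two multiply when both score and visit differ.

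| Between scores | Between visits 0.5 | 0.7 | 0.8 |
|---|---|---|---|
| 0 | 57% | 50% | 46% |
| 0.3 | 54% | 47% | 42% |
| 0.5 | 48% | 42% | 37% |
| 0.7 | 41% | 35% | 31% |
| 0.8 | 36% | 30% | 27% |

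The range is 27-57%. The low end is not a floor: one common correlation of 0.8 among all 20 statistics gives about 23%. The figures take each test's own error rate as 5%. They do not allow for the missing center and period terms, whose effect on that rate cannot be computed from the documents.

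**After reduction to one contrast per score.** Five unadjusted tests give 1 - 0.95^5 = 23% if independent and about 18% at correlation 0.5. With each of the five tested at 0.01, the figure is about 4-5%.

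**What averaging over visits does.** The variance of a mean of k visits, relative to one visit, is (1 + (k-1)rho)/k. For k = 4 this is 0.625 at rho = 0.5 and 0.775 at rho = 0.7, so the SE is 0.79 to 0.88 of the single-visit SE. An effect confined to 24 months would be divided by 4. Its signal-to-noise relative to the 24-month test alone would be 0.25/0.79 = 0.32 to 0.25/0.88 = 0.28. Averaging gains precision for a sustained effect and loses most of a late one.

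**Visit timing.** With enrolment allowed to 12 months after surgery, the 3-, 6- and 12-month forms can all fall before enrolment for some men. Only the 24-month form is after enrolment for everyone. The documents do not give the distribution of enrolment times, so the share of affected forms cannot be computed.

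**The case against.** The waiver is openly prespecified, applies to one of six secondary objectives and leaves the primary test of the GC-score effect untouched. The objective is worded as an investigation, and the analysis paragraph begins with summary statistics, confidence intervals and plots. No success rule is stated. On that reading the p-values are descriptive and a familywise rate is beside the point.

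Much of this stands, and it limits what can be said:

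- A reader might infer that the trial will falsely declare a QOL impact in 64% of null cases. The documents do not support that. No rule makes one p<0.05 a declaration, and 64% requires independence among repeated scores in the same men. Three of the four domains concern erectile or sexual function, so substantial correlation is plausible.
- A reader might count up to 40 tests by adding the Mann-Whitney comparisons. Section 7.3 says "a Mann-Whitney test for differences will be used to corroborate the ANCOVA model", under a stated condition and on the same data, so it is not a separate route to a claim.
- A reader might infer that formal adjustment, such as Holm, or a contrast averaged over visits is required. Both are trade-offs. Adjuvant therapy can start as late as 18 months after surgery (Section 5.1), so an effect could appear late, and the average would dilute it.
- Bias from missing forms is possible, but the documents give no missingness figure, so its size cannot be claimed.

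What the objection does not answer is that the plan never calls these tests descriptive. It puts them at a 0.05 level under a formal secondary objective. Nor does it answer the unused repeated measures or the forms that precede enrolment.

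**Conclusion.** The point holds as a worthwhile improvement to a secondary analysis. The count of 20 tests, the waiver, the absence of a key contrast and the visit-by-visit approach are all in the text, and the expected one false positive in 20 needs no assumption about correlation. The 27-57% figure rests on two assumptions: that any single nominal result would be read as an impact, and that the correlations lie in the ranges tabulated. Even the 23% obtained under one common correlation of 0.8 is more than four times the nominal 5%, so the direction does not depend on the correlation chosen. The enrolment-timing problem follows from Sections 4.1 and 7.3 alone and would remain if the p-values were labelled descriptive.

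**What to change.** In Section 7.3, Secondary Objective 5:

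1. Replace the visit-by-visit ANCOVAs with one repeated-measures mixed model per score, using all available post-enrolment forms. Include arm, visit, arm-by-visit and time since surgery, with the center and period effects of the Section 7.1 model.
2. Define post-enrolment for each man by comparing the form date with his enrolment date.
3. Keep the semiparametric analysis as a sensitivity analysis for skewed data and ceiling or floor effects.
4. Choose one of two statements: name one key contrast per score from this model, or say that the QOL p-values are descriptive. If key contrasts are named, say how the five are read together; read singly and unadjusted they still carry about 18-23%.
5. Report visit-specific differences with 95% confidence intervals, without stand-alone significance claims.

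The change needs SAP wording and a somewhat more complex model, but no new data. Its costs are fewer usable early-visit forms and visit-specific p-values that no longer support claims of their own. If an average over visits is chosen as the key contrast, it dilutes an effect confined to a late visit, so that choice should be made with the expected timing of any effect in mind.
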